This study will consist of electromyography (surface and intramuscular), peripheral nerve stimulation, and transcranial magnetic stimulation, electrical stimulation, of the hand, arm, leg, and foot representation of the primary motor cortex, as well as MRI scans of the brain. We will examine the physiological measurements of upper and lower extremity muscles (such as in the first dorsal interosseous (FDI), biceps brachii (BIC), anterior deltoid (AD), tibialis anterior (TA), hamstring (HAMS) and quadriceps (QUAD)). This study may occur at the Miami Project to cure Paralysis at the University of Miami. We will include subjects between the ages of 18 and 85, both healthy controls and individuals with chronic spinal cord injuries that occurred at least 6 months prior to recruitment. Both healthy controls and those with spinal cord injuries will be able to perform small hand and arm movements and small leg and foot movements. The primary outcome measures of this study are muscle responses to stimulation with magnetic pulses using TMS and electrical stimulation of a peripheral nerve in the arm or leg. We propose to enhance the recovery of motor function by using new protocols of high frequency non-invasive repetitive TMS (rTMS) and motor training. Repetitive TMS will be used during hand, arm, leg and foot movements in a task-dependent manner to induce cortical plasticity and enhance voluntary output of the muscles associated with those movements. Second, rTMS will be applied in a task-dependent manner during a visuo-motor training task that also involves movements of the hands, arms, legs or feet.

Phase 1

Aim 1. Neural Control of Movements in SCI and Control Subjects

We will use TMS, CMEPS, and peripheral nerve stimulation to test the hypotheses that 'precision grip and wrist movements will be associated with reduced motor cortical (as measured by intracortical inhibition) and spinal inputs (as measured by F-wave persistence and amplitude) to hand and wrist motoneurons after cervical SCI compared to controls'. Subjects will be instructed to perform a precision grip (between index and thumb) and simultaneously wrist flexion or extension movements. Measurements of cortical and motoneuronal excitability will be acquired during movement.

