(B). Motoneuronal excitability (reflected by F-wave persistence and amplitude): F-waves will be tested by using supra-maximum stimulus intensity (120% of the maximal motor response) to the ulnar nerve at the wrist and the median nerve at the elbow. The anode and cathode will be approximately 3 cm apart and 1 cm in diameter. We will examine F-waves in first dorsal interosseous, flexor and extensor carpis radialis muscles.

Phase 2

Aim 2a. Enhance recovery of motor function by using non-invasive repetitive transcranial magnetic stimulation (rTMS)

To accomplish this aim we propose to complete two main experiments. First we will use rTMS to test the hypothesis that *rTMS induced cortical plasticity during movement will enhance voluntary output in hand muscles (as measures by electromyography and Jebsen Taylor Test) after spinal cord injury (Aim 2a)*. Second, we will combine precision grip and wrist training with rTMS to test the hypothesis that *precision grip training outcomes will be enhanced by rTMS induced cortical plasticity (aim 2b)*.

Experiment 1 (Aim 2a)

Participants will be randomly assigned to three groups: (1) rTMS, (2) Sham rTMS and (3) sham rTMS over control brain area. Randomization will be performed by lottery (i.e. Drawing from an envelope a piece of paper indicating the intervention). In the first two groups, rTMS stimulation will be targeting finger and wrist muscles during precision grip and write voluntary contractions. In the last group, rTMS will be applied over the dorsolateral prefrontal cortex (DLPFC) or at the leg presentation of the primary motor cortex, or at other related control area as needed. Each subject will be asked to participate in all sessions separated by a washout period of approximately one week. During testing, subjects will be seated in an armchair with both arms flexed at the elbow by 90 degrees. In each group we will use the same apparatus described in Aim1. At the start of the experiment subjects will perform 3 brief MVCs (3-5s) into index finger abduction and wrists flexion and extension, separated by 30 seconds. The maximal forces will be used to set targets for subsequent submaximal contractions.

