Target population:

Male and female veterans with spinal cord injury at least 1 year after injury was sustained. We also plan to enroll control subjects who do not have any history of spinal cord injury.

Inclusion/Exclusion Criteria :

Participants who are unimpaired healthy controls:

- (1) Male and females between ages 18-85 years
- (2) Right handed
- (3) Able to complete precision grips with both hands

- (4) Able to complete full wrist flexion-extension bilaterally
- (5) Able to walk unassisted
- (6) Able to complete full ankle flexion-extension bilaterally

Participants who have had a spinal cord injury:

- (1) Male and females between ages 18-85 years
- (2) Chronic SCI (\geq 6 months of injury)
- (3) Spinal Cord injury at or above L5
- (4) The ability to produce a visible precision grip force with one hand
- (5) Individuals who have the ability to pick up a small object (large paperclip) from a table independently
- (6) Able to perform some small wrist flexion and extension (measured by a goniometer)
- (7) The ability to perform a small visible contraction with dorsiflexor and hip flexor muscles
- (8) No subjects will be excluded based on their race, religion, ethnicity, gender or HIV status.

Exclusion criteria for enrollment For SCI and Healthy Control Subjects (for stimulation):

- (1) Uncontrolled medical problems including pulmonary, cardiovascular or orthopedic disease
- (2) Any debilitating disease prior to the SCI that caused exercise intolerance
- (3) Premorbid, ongoing major depression or psychosis, altered cognitive status
- (4) History of head injury or stroke
- (5) Metal plate in skull
- (6) History of seizures
- (7) Receiving drugs acting primarily on the central nervous system, which lower the seizure threshold (see appendix 2)
- (8) Pregnant females
- (9) Ongoing cord compression or a syrinx in the spinal cord or who suffer from a spinal cord disease such as spinal stenosis, spina bifida, MS, or herniated cervical disk
- (10) Individuals with scalp shrapnel, cochlear implants, or aneurysm clips.

Qualified subjects can participate in up to 190 visits for this study. Visit range from 1-3 hours in length.

Start date: 11/2015.

Completion Date: 12/2019

E. Risks

This is a minimal risk proposal.

TMS procedures:

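### No exclusion covers known peripheral nerve disease in the tested limb, so the Aim 1 F-wave comparison of SCI with controls can read a peripheral lesion as reduced spinal input

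*Combined protocol and SAP*

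**What the plan says.** The section Inclusion/Exclusion Criteria gives one list of ten exclusions for both groups. Above the cord it names, among others, "History of head injury or stroke". At cord and root level it has exclusion (9), "Ongoing cord compression or a syrinx in the spinal cord or who suffer from a spinal cord disease such as spinal stenosis", which goes on to spina bifida, MS and herniated cervical disk. The nearest general item is exclusion (1), "Uncontrolled medical problems including pulmonary, cardiovascular or orthopedic disease". No item names a peripheral nerve or plexus condition.

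The inclusion lists differ by group. Controls appear under "Participants who are unimpaired healthy controls" and need precision grip in both hands and full wrist movement on both sides. SCI participants need a visible grip force in one hand, the ability to pick up a large paperclip, and some small wrist movement.

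C. Study Design, Methodology defines the main endpoints: "The primary outcome measures of this study are muscle responses to stimulation with magnetic pulses using TMS and electrical stimulation of a peripheral nerve". The Aim 1 hypothesis has two halves. The cortical half rests on intracortical inhibition. The spinal half is worded as "spinal inputs (as measured by F-wave persistence and amplitude) to hand and wrist motoneurons after cervical SCI compared to controls". Part (B) of Phase 1 evokes F-waves by stimulation "to the ulnar nerve at the wrist and the median nerve at the elbow". Section G analyses Aim 1 by repeated-measures ANOVA with TASK and GROUP and states no covariate.

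**The concern.** An F-wave travels up the motor nerve to the cord and back down to the muscle. A lesion along that route can lower persistence and amplitude with no change in the motoneuron's excitability or its inputs. Aim 1 interprets exactly that pattern, lower in SCI than in controls, as reduced spinal input.

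GROUP is not randomised in Aim 1, so only eligibility and analysis can keep the groups comparable in the peripheral nerve, and neither addresses it. If lesions are more frequent among tested SCI limbs, the analysis can support the hypothesis for the wrong reason. A larger sample does not help: it makes a fixed spurious difference easier to detect.

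**Working it through.** **Step 1: read every exclusion against the gap.** Exclusions (3) to (6) and (10) concern psychiatric state, head injury, stroke, seizures and metal or implants. Exclusions (7) and (8) concern drugs and pregnancy. Exclusion (9) stops at the cord and the cervical disk. Exclusion (1) applies only when a problem is uncontrolled. Exclusion (2) requires a debilitating disease before the SCI that caused exercise intolerance. An ulnar entrapment, a mild diffuse neuropathy or a past nerve transfer meets none of these as written.

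**Step 2: compare the two inclusion lists.** A peripheral motor deficit that limits grip or wrist range would tend to fail a control, who needs full bilateral function. In an SCI participant, who needs only a visible grip, the paperclip task and small movements, it can pass. Easier entry in one group follows from the written criteria. It does not show that more SCI participants have such a deficit.

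**Step 3: trace which Aim 1 measures are exposed.**
- *F-wave persistence and amplitude:* exposed. The ulnar nerve is stimulated at the wrist. A block at the elbow lies between that site and the cord, so it can reduce the F-wave in first dorsal interosseous while leaving the direct motor response normal. Expressing the F-wave relative to the maximal motor response, which the plan does not state, would not remove this.
- *MEP size:* exposed to a lesser extent. Part (A) of Phase 1 sets TMS intensity to give half of each muscle's own maximal MEP. Half of a reduced maximum is still smaller in absolute terms.
- *SICI:* largely protected. It compares conditioned with test responses in the same person and muscle, with the test response set at 50% of that person's maximum.

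**Step 4: look for a later correction.** Section G states no covariate. The demographic and injury data listed before Target population include level and date of injury, but not nerve status. No nerve-conduction screen is described.

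**Step 5: illustrate how the bias would behave.** The plan has no figure to reproduce. Let p be the excess share of SCI participants with a relevant lesion and d the F-wave deficit among them in between-person SD units. With no true group difference, a two-sided 5% test and n per group:

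- spurious shift = p × d
- SE = √(1 + p(1 − p)d²/2) × √(2/n)
- chance of a false GROUP effect = Φ(shift/SE − 1.96) + Φ(−shift/SE − 1.96)

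The values of p and d, and the 5% level, are assumptions. For n, section F gives up to 250 per group for the whole study and a 25% attrition allowance; 250 × 0.75 = 187.5, taken as 187. Both are ceilings for Aim 1, whose own size is not stated.

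Example, p = 0.10, d = 1.0, n = 250: shift = 0.10; SE = √1.045 × √0.008 = 0.0914; ratio = 1.094; chance = Φ(−0.866) + Φ(−3.054) = 0.194.

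| p | d | Shift (SD) | n = 250 | n = 187 |
|---|---|---|---|---|
| 0 | any | 0 | 5% | 5% |
| 0.05 | 0.5 | 0.025 | 5.9% | 5.7% |
| 0.10 | 1.0 | 0.10 | 19.4% | 15.7% |
| 0.20 | 1.0 | 0.20 | 57.6% | 46.1% |
| 0.30 | 1.0 | 0.30 | 89.1% | 78.8% |

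For scale, 250 per group gives 80% power for a true difference of (1.96 + 0.842) × √(2/250) = 0.251 SD. With fewer participants the false-positive chance falls towards 5%, but the shift itself is unchanged.

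**The case against.** The strongest reply is that the bias needs an excess of relevant lesions in the SCI group, and the documents show none. The age limit of 85 applies to both groups. Wheelchair testing is mentioned only for people who cannot be transferred. A lower movement threshold is what the injury itself requires. This stands: the criteria make an imbalance possible, not established.

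A second reply is that few lesions matter. The Aim 1 muscles are first dorsal interosseous and flexor and extensor carpi radialis. On basic anatomy, a median lesion at the wrist lies beyond the branch to flexor carpi radialis and supplies neither of the others, so it alters no listed Aim 1 measure. An ulnar lesion beyond the wrist stimulation site would also reduce the maximal motor response, which has to be recorded to set the stimulus intensity. This narrows the concern but leaves the ulnar lesion at the elbow untouched.

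Third, there are partial safeguards. The grip and paperclip criteria limit severe denervation of the hand, and the list in exclusion (1) is not exhaustive. The screening question forms named in section H are not among the documents, so a nerve-history question may exist. Even so, no written criterion says what to do with the answer.

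A reader might also infer that the cortical half of Aim 1 is equally compromised. Matching SICI within the person argues against that, although the protection is incomplete: the conditioning intensity is tied to the active threshold, and small responses lie nearer the noise. Nor does the point carry over to Aim 2 with any force, because a stable neuropathy largely cancels in before-and-after change.

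**Conclusion.** The concern holds in a limited form. Known peripheral nerve disease in the tested limb is not excluded, can enter more easily through the SCI criteria, and is not handled in the analysis. The Aim 1 GROUP comparison of F-wave persistence and amplitude, and to a lesser extent of absolute MEP size, therefore has an uncontrolled alternative explanation.

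The table might be read as an estimate of the false-positive risk. It is not one: p, d and the Aim 1 group size are all absent from the documents, and with no excess of lesions (p = 0) there is no bias. It shows only that a modest excess could matter if Aim 1 is large. The conclusion rests on the wording of the criteria and the path of the F-wave, not on those figures.

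**What to change.** For both groups, add an exclusion for known peripheral neuropathy, plexus injury, or nerve or tendon transfer in the limb to be tested, with a matching screening-history question.

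The stated start is 11/2015, completion is 12/2019, and pages carry the date 03/01/19, so a new criterion alone will not reach those already enrolled. For them, take the same history and either drop the affected nerve-muscle pairs from the Aim 1 F-wave and MEP analysis or report a sensitivity analysis without them. Make that decision from history, blind to the F-wave results.

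Do not use an F-wave latency cut-off. Latency can be read only when F-waves occur, so the rule would select on the outcome. The wrist-evoked motor response would not help either, since it can stay normal with a block at the elbow.

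The cost is one eligibility line, one question, and the loss of a small share of SCI participants or muscles from the Aim 1 contrast. Undiagnosed neuropathy would not be removed, and the report should say so.

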The TMS system stimulates the brain non-invasively. It generates a small magnetic field across the subject. TMS is widely used in clinical research, and the risks of TMS are believed to be very low. However, there is the very slight chance that TMS can cause a seizure. There is no ionizing radiation exposure involved and the studies are non-invasive. All participants will be screened before enrollment to assure that they meet study criteria and that there are no contraindications to TMS.

Subjects will be instructed that they can discontinue the TMS experiment at any time. In the unlikely event of a seizure, a medical physician will be contacted for immediate response. If a headache or mild scalp discomfort occurs, subjects will be directed to use over the counter pain medication at their own discretion. Earplugs will be utilized to minimize any type of hearing damage that might possibly occur due to the sound generated by the TMS equipment. [name] (PI) and/or an authorized team member will conduct TMS procedures as needed.

[name] has been working with TMS procedures for the last 13 years and has extensive experience in the use of TMS procedures. Although very unlikely, it is theoretically possible that the participant may have a seizure induced by the TMS. Considering the large number of subjects and patients who have undergone TMS studies since 1998 and the small number of seizures, we can assert that the risk of TMS to induce seizures is certainly very low (see review by Rossi et al., 2009). However, we will inform the participant about this unlikely risk. If a seizure occurs, it will occur during the TMS application itself, not after. When a seizure happens the participant's brain starts acting strangely and participants may feel dizzy and have repetitive rhythmic movements of any part of their body. If this unlikely event happens, we will immediately call an attending physician. On weekends, the subject should call the emergency 24 hour [contact] to get in touch with [name], and let him know that he is a research subject from the Miami VA in Enhancement of Motor Function after Spinal Cord Injury.

In the unlikely event of a seizure, a standard seizure protocol will be followed:

1. Cushion the head and area so subject does not injure themselves.
2. Turn the subject on their side to prevent aspiration
3. Monitor the duration of the seizure

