4. If the seizure ends in less than 60 seconds, monitor and contact the primary care MD to rule out predisposing factors.
5. If the seizure lasts more than 60 seconds, activate emergency services.

In the event that a seizure occurs on premises and we are unable to reach the physician, 911 will be called for emergency services.

Risks of Muscle Activity Recording (EMG): Mild discomfort, such as an itching sensation may be felt under the electrodes that register the response in your muscles. There may be some pain or bleeding from the needles used for intramuscular recording. The possibility of this is infrequent (occurring in 1-10%, or 1-10 out of 100 people). We will clean the area with alcohol and use standard, hospital grade electrodes, and sterile needles.

Peripheral Nerve Stimulation intensity will be increased gradually during the evaluations when necessary. Mild discomfort, such as an itching sensation may be felt under the electrode that stimulates your wrist or under the electrodes that register the response in your muscles. The possibility of this is infrequent (occurring in 1-10%, or 1-10 out of 100 people). We will clean the area with alcohol and use standard,

hospital grade electrodes. Another risk of the nerve stimulation used in this research is that you might feel mild pain, if pain fibers could be activated.

MRI scan: Subjects, investigators, and facility staff will be examined by a hand-held screening device for magnetic material before entry and each re-entry to the scan room. Warning signs, including the specific dangers of high magnetic fields, are posted in the necessary location. The standard 3 Tesla Magnet will be used for testing. The MRI exam involves no exposure to x-rays or radioactivity, and is safe. The FDA approved the Siemens 3-T scanner, which time varying magnetic fields (gradient), specific absorption rate and acoustic noise levels. FDA guidelines will be strictly enforced at our 3T scanner.

JTT/CAHA/pinch grip/ASIA: individuals will have resting periods as needed, all procedures will be explained in detail and subjects will be informed that they can stop the experiment at any time

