Every effort will be made to make sure that the information about you obtained from this study will be kept strictly confidential. Private information is collected about participants as part of this study. Screening forms are filled out by the study coordinator or other approved study team member by phone or in person. Please see all specific questions asked to participants listed in our “SCI Subject Screening Questions” and “HV Screening Questions” forms. Screening forms are used during the screening session to collect both identifiable information as well as non-identifiable information. The research staff will take every precaution to protect all identity and the confidentiality of the information collected about each subject. Any electronic or hard/paper copies of the information collected will be stored in a secured location. Any copies that contain information that could be used to identify participants (such as their name, address, date of birth, etc.), will be stored separately from any information that does not contain identifiers. Only those individuals who are authorized to review the information will have access to it. Identifiable electronic information related to participants’ involvement will be stored on restricted access password protected servers. In order to protect their confidentiality, data that we record about subjects may be sent to the organizations listed above via a secure website, courier and or facsimile. The data that will be shared with the study sponsor will not include any names or any information that may directly identify participants. All data will be coded with the study number, which may include participants’ initials.

Information may also be disclosed to the VA Miami Healthcare System Research and Development Office Staff in order to perform duties related to research administration.

References:

1.0 * Please provide a list of references (Multi-site protocols: You may reference the page numbers in the original protocol):

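### The supplied text schedules the check for TMS contraindications once, before enrollment, and requires no repeat before later TMS visits

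*Combined protocol and SAP*

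**What the plan says.** Section E (Risks), under TMS procedures, sets the timing of the check: "All participants will be screened before enrollment to assure that they meet study criteria and that there are no contraindications to TMS". The list under Inclusion/Exclusion Criteria carries the heading "Exclusion criteria for enrollment For SCI and Healthy Control Subjects (for stimulation"), which ties it both to enrollment and to stimulation. Four of its items describe things that can begin after a person has joined:

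- item 4, "History of head injury or stroke"
- item 6, "History of seizures"
- item 7, "Receiving drugs acting primarily on the central nervous system, which lower the seizure threshold (see appendix 2")
- item 8, "Pregnant females"

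Section H describes the forms used for screening: "Screening forms are used during the screening session to collect both identifiable information as well as non-identifiable information". Section E also names seizure as a possible, very unlikely, effect of TMS. It gives five steps for handling a seizure that staff observe. No section sets a later check of seizures, head injury, stroke, medicines or pregnancy before a TMS visit.

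**The concern.** The exclusions protect people for whom the protocol judges stimulation unsuitable. A check on one day establishes only that a person was suitable on that day. In Aim 2b the active arm then has repeated rTMS over some weeks. Both arms have TMS assessments during training and at three follow-up visits about a month apart. Someone who starts a drug that lowers the seizure threshold, has a seizure or head injury at home, or becomes pregnant in between would look no different on arrival at the laboratory. Unless the participant mentions it, or a staff member happens to ask, the next stimulation may go ahead in a person whom the protocol would have kept out at entry.

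What is at stake is the safety of individual participants.

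**Working it through.** The documents give no total duration for Aim 2b, so there is no stated figure to reproduce for the period after the check. The per-session pulse count can be reproduced.

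**Inputs**

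- Training: about 15 sessions over about 3 weeks (Experiment 2, Aim 2b).
- rTMS dose: 8 blocks of 10 trains of 15 pulses (rTMS protocol, Aim 2a), carried over to Aim 2b as a total of 1,200. I read this total as per session.
- Sham: only a second coil, discharging into the air behind the head, is triggered (training plus sham group).
- TMS assessments: before and after sessions 1, 5 and 10 (plan for long-term effects), then at 1, 2 and 3 months (follow-up). They include MEPs, SICI and IHI.
- MEPs: 30 per condition (Aim 1, TMS measurements). One condition per assessment is counted, so MEP totals are minimums; SICI and IHI pulses come on top.

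**Pulse count.** 8 × 10 × 15 = 1,200 per session, which agrees with the protocol. Over the full course: 15 × 1,200 = 18,000 in the active arm.

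**Time from session 1 to the last TMS visit.** 3 months × (365.25 / 12 / 7 = 4.35 weeks) = 13.0 weeks, and 3 + 13.0 = about 16 weeks. With 4-week months it is 15 weeks. The interval from screening to session 1 is not stated and would add to this.

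**Spacing.** 15 sessions / 3 weeks = 5 a week, so gaps during rTMS are days. Gaps between follow-up visits are about 4.35 weeks.

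**Visits with TMS to the head in Aim 2b.** Active arm: 15 + 3 = 18. Sham arm: sessions 1, 5 and 10 plus three follow-ups = 6.

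**Stimulation still to come when an exclusion arises**

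| When it arises | rTMS left, active arm | rTMS left, sham arm | TMS assessments left, both arms | MEP pulses left, minimum |
|---|---|---|---|---|
| Between sessions 1 and 2 | 14 × 1,200 = 16,800 | 0 | 2 (session 5) + 2 (session 10) + 3 = 7 | 7 × 30 = 210 |
| Between sessions 10 and 11 | 5 × 1,200 = 6,000 | 0 | 3 | 3 × 30 = 90 |
| After session 15, before month 1 | 0 | 0 | 3 | 3 × 30 = 90 |

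The largest rTMS exposure therefore follows an event in a short gap early in training. The longest gaps, where an event is most easily missed, come before assessment pulses only. Those pulses are not all weak: the IHI conditioning pulse is set above resting motor threshold.

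**The case against.** The strongest reply is that the gap is read from silence. Section E says when screening happens; it does not say that nobody asks again. The screening forms and appendix 2 are referred to but not supplied, and the consent pages, a natural place to ask participants to report a new drug or a pregnancy, were removed. A reader might infer that contraindications are checked once only and that a later event would go unnoticed. The documents do not support that. They support the narrower statement that no repeat is required in the text supplied.

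There is also a reporting route. Section E tells participants about the seizure risk and gives a 24-hour emergency contact for weekends, so some seizures away from the laboratory may come to light. That stands, and it is why the event *may* be missed. But the route depends on the participant calling, is set out for seizures, and does not make the next session conditional on anything.

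Nor does the protocol tell staff to stimulate someone known to meet an exclusion. The heading refers to stimulation, and item 7 is in the present tense. A careful investigator who knew would stop. The gap is in how the investigator comes to know.

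A contrast with MRI is tempting, because there everyone is "examined by a hand-held screening device for magnetic material before entry and each re-entry to the scan room". It adds little: that is a scan-room check for metal which also applies to staff, not a repeat of eligibility, and it does not show that TMS screening was meant to happen once. The sentence on screening forms is likewise weak evidence, since it sits in the privacy section and sets no limit on later checks.

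Finally, the protocol calls the study minimal risk and sets rTMS at 80% of active motor threshold. That bears on how serious the point is. It does not remove it, because the protocol still excludes these people and the same reasoning applies at session 10 as at session 1.

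**Conclusion.** The point holds in limited form: one scheduled check before enrollment, no required repeat, and about 16 weeks in Aim 2b from session 1 to the last TMS visit. What remains after a missed exclusion ranges from 14 rTMS sessions and 7 TMS assessments (active arm, event after session 1) to 3 assessments (either arm, event after training). It is a cheap improvement in participant safety.

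Three stronger readings should be avoided.

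- A reader might take the 16 weeks as continuous stimulation. It is about 3 weeks of rTMS in one arm, then three follow-up visits with test pulses over about 13 weeks.
- A reader might infer bias in the group comparison. None is claimed or shown.
- A reader might infer that stimulation could resume after a seizure in the laboratory, because the seizure steps do not address it. That is weak, since item 6 already points to stopping.

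The documents give no rate for seizures, new drugs, injuries or pregnancy in this population, so no number of affected participants can be offered. The figures assume exactly 15 sessions, 1,200 pulses in each, calendar months and one MEP condition per assessment. The conclusion covers the supplied text only.

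**What to change.** Keep the existing seizure steps and add a paragraph to section E along these lines:

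> Before each visit with TMS or rTMS, staff ask about any seizure, head injury, stroke, new or changed medicines (checked against appendix 2) and possible pregnancy since the last visit. If any answer is yes, no TMS, rTMS or CMEP stimulation is given until a physician has reviewed it against exclusions 4, 6, 7 and 8. A participant who has a seizure after enrollment meets exclusion 6 and receives no further TMS, rTMS or CMEP stimulation. Training without stimulation and behavioral and clinical measures may continue; F-waves and EPT continue only if the reviewing physician agrees. The participant stays in the assigned group for analysis.

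CMEPs are named because they use supramaximal electrical stimulation behind the mastoid. F-waves and EPT are left to the physician because they are electrical stimulation too, and the exclusion heading does not say which kinds of stimulation it covers. If the screening forms or a site procedure already require such questions, a cross-reference in section E is enough.

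The cost is a few questions at each TMS visit, with no added visits or procedures. A participant who is stopped contributes no further TMS outcomes. Section G does not say how an incomplete series enters the repeated-measures ANOVA, so a sentence on that would be useful alongside.
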